12. ECONOMIC EVALUATION DESIGN

12.1. Aims, Objectives and Research Questions

Aims

The primary aim of the economic evaluation is to develop an understanding of the overall net value to the public sector of impacts associated with the proactive phone calls and signposting to services. To ensure that the evaluation is comprehensive, we will consider the perspective of all major public sector stakeholders (including both central and local government). However, decisions about implementing the intervention are likely to be taken by individual LAs and, if the benefits exceed the costs for the LAs, then this could provide a strong case for investment at the local level. Therefore, as a secondary aim, we will take an LA costing perspective, considering the overall net value to the LA.

In addition to the aims set out above, we expect that CHI will combine the findings from this evaluation with those from other interventions piloted within the wider Test and Learn programme. This could provide robust evidence on the relative advantages and disadvantages of different approaches to preventing homelessness. In particular, the monetary value calculations undertaken as part of this evaluation will contribute to the formation of a consensus-based set of values for the key costs of homelessness and for the cost savings resulting from its avoidance. This evidence will support LAs and other public stakeholders in making informed policy decisions about homelessness prevention in future.

Objectives

- Identify the relevant public sector costs of delivering the intervention, compared to the counterfactual scenario (BAU), including:
 - *Direct costs* to the participating LAs – that is, costs in relation to building and implementing the predictive model using the OneView data platform, and of preparing for and delivering the intervention phone calls. We will distinguish between upfront costs (e.g. setting up the platform, training for the call handlers) and ongoing costs (e.g., maintaining the platform, making the calls).
 - *Direct costs* of the OneView platform license fee. We will split the direct cost of the OneView platform between the intervention and other potential uses of the platform by the participating LAs, if the LAs are using it for other functions as well.
 - *Indirect costs* to the participating LAs – that is, costs in relation to providing support services to at-risk individuals from households identified by the model, beyond the initial intervention phone call delivered by the LA. This will include

the costs of any follow-up phone calls made by the call handler and costs of the support service(s) taken up as a result of the intervention signposting.

- Identify the cost savings to the public sector resulting from the intervention. This will include cost savings that arise either directly due to members of beneficiary households avoiding homelessness or indirectly – where avoided homelessness leads to another ‘downstream outcome’, such as better health, which then creates cost savings.
- Review and collate evidence linking the number of beneficiary households to the probability of accruing the costs/cost savings identified above.
 - *Beneficiary households* are the households at risk of homelessness (per the predictive model), whose members avoid being owed a relief duty because they have become homeless. This is intended to align with the definition of *intervention impact* – the number of beneficiary households – to be measured through the impact evaluation.⁴
- Assess the overall Value for Money delivered by the intervention.

Research Questions

Our overarching question is whether the intervention provided value for money. In order to answer it, we will investigate the following four research questions:

1. How much was the overall cost to the public sector of delivering the intervention? This will consider costs to the participating LAs over and above business as usual, including both direct and indirect delivery costs, as well as the license fee for the Xantura OneView platform provided to the LAs to enable the intervention.
2. How much money is saved by the public sector as a result of fewer households being owed a relief duty because they have become homeless?

⁴ The project impact will be measured in terms of number of households who avoid being owed a relief duty because they have become homeless. For the purpose of the economic evaluation, this impact measure can be applied directly to those cost/cost saving values which are expressed on a per household basis. In case of values expressed on a per person basis, a suitable adjustment will be made depending on the nature of the cost/cost saving in question. For example, a conservative assumption of a single individual beneficiary per household could be applied to employment-related benefits, whereas all household members (assuming an average household size) could be considered in relation to NHS-related benefits.

3. How much money is saved by the LA as a result of fewer households being owed a relief duty because they have become homeless?
4. What was the net value of delivering the intervention, per beneficiary household? *Net value* represents the difference between the cost savings created by the intervention and cost of delivering the intervention, over and above the counterfactual.

12.2. Research Design and Methods

Overall Approach

Given the economic evaluation's focus on the public sector costs and cost savings associated with the intervention, and the wider aim of comparing the relative performance of different Test and Learn interventions, the intervention's Value for Money will be assessed using **Cost Effectiveness Analysis** (CEA). This will involve calculating the intervention's cost effectiveness ratio (delivery cost of intervention vs business as usual, per beneficiary household) - and comparing it against the following reference points:

- other initiatives within the wider Test & Learn and Systems-Wide Evaluation Programme (subject to availability of the relevant evaluation results)
- a breakeven benchmark given by the cost savings for the public sector per one beneficiary household.

To be considered good value for money, the intervention would be expected to have a cost efficiency ratio below the breakeven benchmark. This would indicate that the intervention has:

1. created a positive impact by reducing the number of at-risk households whose members are owed a relief duty because they have become homeless, compared to the counterfactual, and
2. reduced public spending by more than it cost to deliver, compared to the counterfactual.

Relevant Alternatives/ Counterfactuals

The intervention costs, including cost savings, will be assessed relative to a counterfactual BAU scenario.

The definition of this counterfactual scenario will be aligned with the impact evaluation approach, to ensure that both the beneficiaries and the intervention costs are assessed in a consistent way. The counterfactual will be represented by the control group of the RCT, who will receive standard homelessness prevention and support services offered by the LAs participating in the project to individuals at risk

of homelessness. Unlike the treatment condition, participants receiving BAU will not receive a phone call from the LA referring them to relevant support services.

Evaluation Perspective and relevant stakeholders

The proposed approach to the economic evaluation considers the costs and cost savings associated with the intervention. Costs and cost savings will be assessed focusing on the perspective of all major public sector stakeholders (LAs, Central Government and the NHS), acknowledging their wider impacts on the society, in particular on the quality of life of the individuals affected; as well as from the LA perspective.

Time Horizon

We will follow CHI's guidance on the evaluation time horizon to ensure consistency with other interventions within the wider Test and Learn programme. In line with that guidance, this economic evaluation will consider all costs and cost savings accruing throughout the time period of the impact evaluation (January 2024 – January 2025).

We will provide estimates of the cost saving unit values (see Table 10 for further details) on a per household / per person per year basis and apply these in line with the evaluation time horizon. Where relevant (and supported by appropriate evidence), we may consider either a shorter or a longer time horizon – e.g. in case of cost savings sustained in the long term. Where this is the case, we will consider a range of plausible time horizons as part of the sensitivity analysis.

In case we find that the intervention costs exceed the cost savings within the core evaluation time horizon, we will include a break-even analysis over time. This will consider a scenario where the intervention is continued on an ongoing basis, applying the intervention to further cohorts of at-risk households over subsequent years. As part of this break-even analysis, we will carry out an assessment out of the level of intervention impacts (in terms of fewer households being owed a relief duty because they have become homeless), intervention costs, and cost savings that would apply in subsequent years of the intervention.

Costs

Costs of delivering the intervention include all of the following: direct costs of the Xantura OneView platform license fee, direct LA costs of staff time spent on setting up the predictive model to identify individuals at risk of homelessness using OneView data platform, direct LA costs of ongoing maintenance and monitoring of the platform, direct LA costs of the preparation and delivery of the intervention phone calls, and indirect LA costs of providing proactive support to members of at-risk households assigned to the RCT treatment group.

Costs of delivering the counterfactual include only the indirect LA costs of providing business as usual support to members of at-risk households assigned to the RCT

control group. If we see significant variation between LAs we will report the range of costs with, where available, information about the factors that seem to drive greater BAU costs.

These costs are expected to accrue directly to the LAs participating in the project. However, given the project's RCT implementation structure, each LA will be providing services simultaneously to the intervention and control groups – whilst funding them through a range of sources, including:

- Unitary/Lower-tier LA own budget
- Upper-tier LA funding
- MHCLG Rough Sleeping Initiative grants,⁵ a multi-year programme providing local councils with long-term funding to support those sleeping rough or at risk of rough sleeping
- Other central government funding.

Therefore, it would not be practical to differentiate between the intervention and BAU delivery costs according to their funding source. Instead, we recommend that these costs are assessed based on spending data collected from the participating LAs through the dedicated Cost Data Submission Tool.

The table below provides further detail on the spending categories to be considered as part of the Cost Data Submission Tool.

Table 9: Economic Evaluation costs

Cost	Supplementary Data Source	Notes
Intervention only		
Direct costs OneView platform license fee (market value) LA resources (salaries, time, overheads, fees) spent on: Setup, monitoring and maintenance of OneView data Call handler training Casework (intervention phone calls providing proactive support) Administration of intervention	Cost Data Submission Tool*	
Intervention and counterfactual		

⁵ [Rough Sleeping Initiative: 2022 to 2025 funding allocations](#)

Indirect costs LA resources (salaries, time, overheads, fees) spent on: Running cost of existing support services	Cost Data Submission Tool* Can be triangulated against relevant Simetrica-Jacobs exchequer values ⁶ estimated for the HACT UKSVB ⁷	To be apportioned according to service uptake in intervention and control groups ⁸
--	---	---

** LAs will be provided with a comprehensive **cost** form to populate. A copy of the Cost Data Submission Tool will be provided separately.*

Benefits (and averted costs)

The intervention aims to benefit society by reducing the number of at-risk households whose members are owed a relief duty because they have become homeless. We will capture the value of these benefits through proxy measures that focus on the resulting financial implications for the LAs and the central government, such as avoided spending on temporary accommodation and reductions in Council Tax debt, or the averted costs of housing support, healthcare expenditure and unemployment benefit payments. These proxy measures effectively represent resources that become freed up thanks to the intervention, and that can be invested to create social value for others in society.

We will estimate cost savings resulting from the intervention in relation to the following key outcomes:

- Reduced need for temporary accommodation
- Reduced Council Tax debt
- Reduced Council housing rent arrears
- Reduced need for emergency relief services

⁶ E.g. provision of housing, financial and debt advice.

⁷ The HACT UKSVB exchequer values have been developed by piecing together various sources of evidence linking outcomes such as housing quality, employment or health to data on public expenditure. It is an approach that relies on a range of judgements and assumptions that allow the quantification of an outcome's financial implications for the government, such as increased tax revenue and cost savings from reduced healthcare expenditure. Details of these assumptions will be provided alongside the relevant monetary values applicable to this evaluation.

⁸ Subject to availability of data on the relevant uptake rates; our understanding is that this may vary depending on the type of support service – e.g. data on the use of Council-run services around debt/Council Tax are likely to be available through the OneView platform, but data on the use of third-party services would be more difficult to obtain.

- Increased financial support to gain/maintain secure housing in the social rented sector
- Increased financial support to gain/maintain secure housing in the private rented sector
- Avoided loss of full-time employment
- Avoided deterioration in overall health

These cost savings will be applied – as appropriate – either to the number of beneficiary households or to the relevant number of affected individuals across all beneficiary households estimated through the impact evaluation using a range of plausible linkage assumptions based on the literature⁹ and Simetrica-Jacobs' prior experience. Using the outcome of employment as an example, if we find through the impact evaluation that the intervention helped 10 at-risk households avoid being owed a relief duty because they have become homeless, this will be combined with an estimated number of individual members of those 10 households who remain employed and would not have been able to do so had they become homeless.

Note that some of the outcomes listed above may have interlinked financial consequences for different public stakeholders. Where these costs/cost savings balance out between different public sector stakeholders, this will be reflected in the analysis (whilst highlighting those that are applicable at the LA level, in line with the overall aims of the evaluation). For example:

- Each at-risk household whose members avoid being owed a relief duty because they have become homeless will result – with some probability – in the LA avoiding the need to provide them with temporary accommodation (a cost saving to the LA).
- At the same time, these household members now have a place to live, either in the social or the private sector, and – again, with some probability – pay for their housing with the help of Universal Credit/Housing Benefit (a cost to the central government).
- Finally, if these household members ends up living in council-owned social rented accommodation, then their rent payments represent a benefit to the LA.

The following table provides further details on the data sources we envisage as a basis for estimating unit values (per household / per person, per year) of the cost savings associated with the outcomes listed above.

Table 10: Economic Evaluation cost savings

⁹ See, for example:

https://assets.publishing.service.gov.uk/government/uploads/system/uploads/attachment_data/file/944598/Initial_findings_from_the_rough_sleeping_questionnaire_access.pdf

Cost savings	Supplementary Data Source	Notes Relevant outcome
Local authority spend on temporary accommodation (2022-2023)	Local authority revenue expenditure and financing England: 2022 to 2023 individual local authority data - outturn, MHCLG	Reduced need for temporary accommodation
Council tax arrears	Xantura predictive model data – based on LA Council Tax arrears records, split by intervention and control group	Reduced Council Tax debt
Council housing rent arrears	Xantura predictive model data – based on LA records on Council housing rent arrears, split by intervention and control group	Reduced Council housing arrears
Emergency relief services annual budget	https://www.mannasociety.org.uk/ within Crisis report (2016), p.26 ¹⁰	Reduced need for emergency relief services ¹¹
Average weekly (social and affordable) rent (2022/23)	Live tables on rents, lettings and tenancies 2022/23, MHCLG	Increased financial support to gain/maintain secure housing in the social rented sector
Government expenditure on housing element of Universal Credit (GB) (2022/2023)	Benefit expenditure by country and region, 1996/97 to 2022/23, DWP	Increased financial support to gain/maintain secure housing in the private rented sector
Cost of unemployment benefits	Based on Simetrica-Jacobs' exchequer values estimated for the HACT UKSVB	Avoided loss of full-time employment

¹⁰ The report uses the annual cost data, which is published by a day centre in London, seeing between 150-180 single homeless people per day and with an annual budget amount reported.

¹¹ This may not constitute a cost to the public sector if the services are provided e.g. by a housing association.

Cost of NHS services for those in poor overall health	Based on Simetrica-Jacobs' exchequer values estimated for the HACT UKSVB	Avoided deterioration in overall health
---	--	---

Note: The outcome-level estimates considered above will be triangulated against other existing estimates of the overall costs of a homelessness application, e.g. from the GMCA Unit Cost Database or the upcoming research from LSE/MHCLG.

Sensitivity Analyses

Sensitivity analysis will aim to reflect the level of estimation uncertainty around key components of the economic evaluation calculations, including (where relevant):

- Number of beneficiary households – e.g. using confidence intervals around the central impact estimates from the impact evaluation
- Cost of delivering the intervention – e.g. using a high-low range of additional intervention implementation costs to the LAs, depending on the variation in responses to the Cost Data Submission Tool (see more details in section 12.3)
- Unit values of the cost savings – e.g. applying fixed band of +/- a suitable percentage around the estimate (we will determine a suitable level for this banding based on the variation in cost savings estimates established through the triangulation analysis)
- Parameter assumptions on the cost savings probability per beneficiary household – e.g. using a range of parameter estimates from different sources.

For presentation purposes, we will rank the sources of uncertainty listed above according to their level of impact on the economic evaluation calculations. If practical, we will provide a combined worst-case/ best-case scenario VfM analysis to illustrate the joint impact of the individual sensitivity ranges considered.

Optimism Bias Assessment

We will follow CHI guidance to ensure consistency with other interventions within the wider Test and Learn programme. We will apply optimism bias adjustments in the recommended 10-15% range to the cost data and noted within the VfM assessment.

Other considerations

For all intervention costs and cost savings extending beyond one year, we will use the HMT Green Book recommended 3.5% discount rate for calculating present values.

We will appropriately uprate all costs and cost savings to a common price base, where necessary, using up to date ONS RPI All Items Index data.

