12.3. Data Collection and Processing

Data Sources

We will collect data on the intervention costs from the LAs through a Cost Data Submission Tool and triangulate these – where relevant and applicable – with appropriate external data sources. The study's impact evaluation will provide estimates of the number of beneficiary households (households whose members avoid being owed a relief duty because they have become homeless) required for the estimation of cost savings resulting from the intervention.

Data Collection Procedures

A Cost Data Submission Tool in the format of an Excel file will be developed by Simetrica-Jacobs. This will be distributed to the LAs participating in the project as part of the IPE's qualitative data collection process (TBC).

The cost estimates obtained from returned submissions forms will be scaled up in line with the project target population in each LA to represent the whole project.

Data Collection Schedule

- Cost data submission form developed – 30th September 2024 (Simetrica-Jacobs)
- Cost data submission form sign-off – 30th October 2024 (CHI/consultation with LAs - TBC)
- Cost data submission form distribution – TBC

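### The value-for-money cut-off works only when the estimated impact is positive: with a negative estimate and a positive incremental cost it is always met, because positive impact is worded as a consequence of the ratio and not as a condition

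*Protocol*

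**What the plan says.** Protocol section 12.2 (Overall Approach) defines the ratio as "delivery cost of intervention vs business as usual, per beneficiary household" and compares it with "a breakeven benchmark given by the cost savings for the public sector per one beneficiary household". The verdict is: "To be considered good value for money, the intervention would be expected to have a cost efficiency ratio below the breakeven benchmark". (The section uses both cost effectiveness ratio and cost efficiency ratio; I read them as the same quantity.)

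It then says that a ratio below the benchmark would indicate two things: that the intervention has "created a positive impact by reducing the number of at-risk households whose members are owed a relief duty because they have become homeless", and that it has "reduced public spending by more than it cost to deliver, compared to the counterfactual".

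The denominator comes from the trial. Section 12.3 states: "The study's impact evaluation will provide estimates of the number of beneficiary households". Section 12.1 likewise aligns the number of beneficiary households with the impact measured by the impact evaluation. Research question 4 in section 12.1 asks: "What was the net value of delivering the intervention, per beneficiary household". Section 12.4 lists net present value per beneficiary household and the ratio as summary outputs. The sensitivity analyses in section 12.2 suggest, as an example, varying the number of beneficiary households "using confidence intervals around the central impact estimates from the impact evaluation".

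I found no statement of what happens to the ratio or the per-household net value if the estimated impact is zero or negative.

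**The concern.** The cut-off is the stated test for the evaluation's overarching value-for-money question. The protocol treats a ratio below the benchmark as evidence that relief duties fell and money was saved. A ratio with an estimated difference in its denominator cannot carry that inference, because dividing by a negative number reverses the inequality. Applied literally, the cut-off is met when the treatment arm has more relief duties than control, and the net value per household then has the wrong sign. Section 12.2 also compares the ratio with other Test and Learn projects, where a negative ratio would look cheapest.

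**Working it through.** **Inputs.** C is incremental delivery cost against business as usual. N is the number of households avoiding a relief duty, from the trial. B is the public saving per beneficiary household. The ratio is R = C/N, and the cut-off is R < B.

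Section 12.2 (Costs) places licence, set-up, maintenance and call costs on the intervention only, and gives business as usual only indirect support costs. So C > 0 is expected. The protocol gives no figure for C or B. I take B > 0 and use assumed amounts below.

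**Sign check.**
- N > 0: R < B is equivalent to B×N − C > 0, as section 12.2 says.
- N < 0: multiplying by N reverses the inequality, so R < B is equivalent to B×N − C < 0. With C > 0 and B > 0 this always holds.
- N = 0: R and (B×N − C)/N are undefined.

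**Numbers.** Assume C = £100,000, B = £5,000 and 1,000 treated households (the treatment arm in Scenario C, Table 7). N is 1,000 times the risk reduction.

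| Reduction | N | R = C/N | R < B? | Total net value B×N − C | Net value per beneficiary household |
|---|---|---|---|---|---|
| +5 pp | 50 | £2,000 | yes | +£150,000 | +£3,000 |
| +0.5 pp | 5 | £20,000 | no | −£75,000 | −£15,000 |
| −0.5 pp | −5 | −£20,000 | yes | −£125,000 | +£25,000 |
| −5 pp | −50 | −£2,000 | yes | −£350,000 | +£7,000 |

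Over a grid with C of £100,000 or £500,000, B of £5,000 or £20,000, 750 or 1,000 treated, and effects of −0.5, −2 and −5 pp (2×2×2×3 = 24 scenarios), all 24 met the cut-off. Total net values ran from −£118,750 to −£1,500,000. The sign result does not depend on the amounts chosen.

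**How likely is a negative estimate?** For control risk p and true reduction d with n per arm, SE = √[p(1−p)/n + (p−d)(1−p+d)/n], and the chance of a wrong sign is Φ(−d/SE). Scenario C gives 1,600 analysed, or 800 per arm. As a check on this input, 800 per arm at 80% power gives a detectable difference of about 2.0 pp at 3% base risk and 7.0 pp at 50%, which agrees with the protocol's 2–7 pp.

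With no effect the chance is 50%. With d = 2 pp and n = 800:

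| Control risk | Wrong sign | Lower 95% limit below zero |
|---|---|---|
| 5% | 2% | 47% |
| 10% | 8% | 71% |
| 30% | 19% | 86% |
| 50% | 21% | 88% |

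Section 5.2 excludes Test Valley from the primary analysis. Assuming three authorities of 500 less 20% attrition, 3×500×0.8 = 1,200, or 600 per arm. At 50% control risk the wrong-sign chance is then about 24%.

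**If confidence limits were carried into the ratio.** Take an estimate of 3 pp, 800 per arm and 50% control risk. SE = √[(0.25 + 0.47×0.53)/800] = 0.025 and the half-width is 4.9 pp, so the limits are −1.9 and 7.9 pp and N runs from −19 to 79 around 30. R is £100,000/(−19) = −£5,263 at the lower limit, £3,333 at the estimate and £1,266 at the upper limit. All three are below £5,000, and the estimate lies outside the two limits. Total net value runs in order: £5,000×(−19) − £100,000 = −£195,000, then +£50,000, then +£295,000.

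**The case against.** The best defence is that section 12.2 clearly wants a positive impact. It says the intervention would be expected to meet the cut-off, which reads more like a necessary than a sufficient condition, and it names reduced homelessness in the next lines. A reader might infer that the protocol sets out to call a harmful result good value. It does not, and the intent stands in its favour. But positive impact is written as something that the ratio indicates, and that deduction fails for negative N.

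Second, beneficiary households are defined as households that avoid a relief duty, and a count cannot be negative. On that reading the ratio does not exist under harm, and the protocol still gives no rule. Since sections 12.1 and 12.3 take the number from the impact estimate, a negative value can arise.

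Third, totals are in the plan. Research questions 1 and 2 ask for overall cost and savings, the section 12.4 calculation tab produces both, and section 12.2 (Time Horizon) compares them. An analyst would probably notice harm. However, that comparison only triggers a break-even analysis over time; it does not override the verdict.

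Two stronger readings should be set aside. One is that the rule wrongly scores a modest benefit as poor value. It does not: for N > 0 the cut-off is equivalent to positive total net value, so the +0.5 pp row fails either way. The other is that the plan commits to putting confidence limits through the ratio. They are offered only as an example, where relevant, and could equally be applied to total savings.

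**Conclusion.** The statement in section 12.2 about what a ratio below the benchmark indicates is wrong as written. It holds for a positive impact estimate, fails for every negative one when incremental cost and benchmark are both positive, and is undefined at zero. Net value per beneficiary household has the same fault. If incremental cost were negative as well, the cut-off would no longer always be met, but it would be met exactly when total net value is negative, so it would still point the wrong way.

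The size depends on the base rate. A reader might take the chance of 21% to 24% at 50% control risk as general; it falls to about 2% at 5%. Footnote 3 to Figure 3 supports a rate of at least 50% only if the predictive model works as stated, and section 9.1 says that little is known about how well it does. All amounts in pounds are assumptions.

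The fault is confined to the economic verdict and its per-household outputs. Randomisation, data collection and the primary estimate are unaffected. It should be corrected before the value-for-money calculation is run.

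**What to change.** - In section 12.2, base the verdict on total incremental net benefit: households avoiding a relief duty × saving per household, minus incremental cost. Call the intervention good value only if this is above zero and the estimated impact is positive.
- Carry the impact confidence interval through this formula. It is linear in the impact, so the limits stay in order and can be read across zero.
- Report the cost per beneficiary household and the net value per beneficiary household (research question 4 in section 12.1, Outputs tab in section 12.4) only when the impact estimate is positive. Otherwise report total cost, total savings and total net value.
- Reword section 12.2 so that a positive impact is a precondition for using the ratio, not something the ratio indicates.

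The cost is wording in sections 12.1, 12.2 and 12.4 and one spreadsheet formula; no new data are needed. The downside is that, with a null or negative impact estimate, the ratio may not be reportable for comparison with other Test and Learn projects.
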